1.2.2.2 HEALTHY SUBJECT PHARMACOKINETIC STUDIES

In parallel with the Phase 1 single-arm, dose-escalation study in subjects with relapsed or refractory hematologic malignancies; two healthy subject, crossover, bioequivalence pharmacokinetics studies have been completed. The first pharmacokinetic study was a Phase 1 drug-food interaction study with a single 200 mg oral dose of umbralisib in healthy volunteers followed by a second single dose Phase 1 pharmacokinetic study evaluating the absorption, distribution, metabolism and excretion characteristics of two different oral formulations of 200 mg umbralisib (original formulation vs. micronized formulation) in healthy volunteers.

1.2.2.2.1 TGR-1202-PK101: FOOD EFFECT

Study TGR-1202-PK 101 was two-period, randomized, two-way crossover, drug-food, drug-gender interaction study in 24 healthy subjects (12 males and 12 females) to assess the mean plasma umbralisib concentration over time following a single oral dose of 200 mg of umbralisib

under fasting and fed condition using the original formulation. In general, administration of umbralisib under fed conditions results in a higher rate of exposure relative to when the product was given under fasting conditions.

The statistical comparisons of umbralisib pharmacokinetic parameters under fasted and fed condition are shown below.

Parameters	Geometric LS Means		% Geometric Mean Ratio	Confidence Interval
	Fasting	Fed		
AUC _{0-t} (ng·hr/mL)	6029.87	9692.02	160.73	140.25 – 184.21
AUC _{0-inf} (ng·hr/mL)	8391.35	14047.17	167.40	141.59 – 197.92
C _{max} (ng/mL)	176.78	483.15	273.31	234.04 – 319.17

Food increased both the extent and rate of exposure of umbralisib. The extent (AUC_{0-t}) and total extent (AUC_{0-inf}) of exposure increased by 61% and 67%, respectively, when umbralisib was administered under fed conditions compared to fasting conditions. The peak plasma levels of umbralisib increased by over 173% when umbralisib was administered with food.

Using these mean values, a 334 mg oral dose of umbralisib under fasted condition can be extrapolated to be equivalent to an oral dose of 200 mg of umbralisib under fed conditions in terms of exposure based on AUC_{0-inf}.

1.2.2.2.2 TGR-1202-PK102: FORMULATION EFFECT

Study TGR-1202-PK 102 was a two-period, randomized, two-way cross over, relative bioavailability and pharmacokinetic bioequivalence study with two different drug product formulations of umbralisib. In this study, umbralisib was administered under fasted conditions in 24 healthy subjects (12 males and 12 females) to assess the mean plasma umbralisib concentration over time following a 200 mg single dose of the original drug product formulation and modified (micronized) drug product formulation of umbralisib. The mean rate and extent of exposure to umbralisib were higher following administration of the micronized drug product formulation compared to the original drug product formulation as mean concentrations were higher throughout most of the sampling interval.

[figure not shown]
Parameters	Geometric LS Means		% Geometric Mean Ratio	Confidence Interval
	Original Formulatio	Micronized Formulatio		
AUC _{0-t} (ng·hr/mL)	5906.11	9439.82	159.83	149.43 – 170.95
AUC _{0-inf} (ng·hr/mL)	7715.67	12378.19	160.43	146.49 – 175.70
C _{max} (ng/mL)	166.20	371.70	223.65	202.33 – 247.20

The micronized drug product formulation increased both the extent and rate of exposure of umbralisib under fasted conditions. The extent (AUC_{0-t}) and total extent (AUC_{0-inf}) of exposure both increased by 60%, respectively, following administration of the modified drug product formulation relative to original drug product formulation. The Peak plasma (C_{max}) levels of umbralisib increased by over 124% following administration of the micronized drug product formulation relative to original drug product formulation under fasted conditions.

Using these mean values, a 320 mg oral dose of umbralisib in the original formulation under

fasted condition can be extrapolated to be equivalent to an oral dose of 200 mg of the original formulation umbralisib under fasted conditions in term of exposure based on $AUC_{0-\infty}$.

The improved exposure seen with the micronized formulation of umbralisib was confirmed in subjects in the Phase 1 dose escalation as well. The chart below illustrates the pre-dose plasma concentrations of umbralisib on Day 1 of Cycle 2 in subjects administered equivalent doses of either the initial formulation in the fasting state or the micronized formulation in the fed state:

1.3 UBLITUXIMAB

Ublituximab is a novel third generation chimeric anti-CD20 monoclonal antibody bioengineered for potent activity, exhibiting a unique glycosylation profile with a low fucose content, designed to induce superior antibody-dependent cytotoxicity (ADCC). Ublituximab exhibits competitive complement-dependent cytotoxicity (CDC), on par with rituximab, and has also been demonstrated to induce programmed cell death (PCD) upon binding to the CD20 antigen on B-lymphocytes. Ublituximab has a unique protein sequence, and targets epitopes on CD20 not targeted by rituximab or ofatumumab, both currently approved anti-CD20 antibodies (Esteves IT, 2011).

1.3.1 PRE-CLINICAL DEVELOPMENT OF UBLITUXIMAB

1.3.1.1 IN-VIVO ACTIVITY

In an in-vitro assay using B-CLL cells from subject donors, ublituximab demonstrated an enhanced ability to kill CLL cells compared to rituximab. Ublituximab demonstrated improved Fc γ receptor IIIA (Fc γ RIIIA)/CD16 binding and Fc γ RIIIA dependent effector functions compared to rituximab. Additionally, ublituximab induced higher in vitro ADCC against CLL cells, and a higher Fc γ RIIIA mediated interleukin-2 (IL2) production by Fc γ RIIIA+ Jurkat cells (de Romeuf C, 2008). Ublituximab demonstrated high ADCC against both subject-derived CLL cells and NHL cell lines. Ublituximab's engagement to Fc γ RIIIA triggers a stronger NK cell cytotoxicity against CLL as compared to rituximab (in vitro) despite CD20 density, likely related to the glycosylation pattern (de Romeuf C, 2008).

1.3.1.2 IN VIVO ACTIVITY

The antitumor effect of ublituximab was compared to that of rituximab with chemotherapy in follicular lymphoma (FL), and mantle cell lymphoma (MCL) xenograft murine models. Single agent ublituximab demonstrated dose-related anti-tumor activity with 100% tumor growth inhibition in

the FL xenograft at a dose of 100mg/kg, and a superior tumor growth delay (21 days) compared to rituximab. Ublituximab also demonstrated superior anti-tumor activity compared to rituximab against MCL xenografts at all dose levels (Esteves IT, 2011).

1.3.1.3 TOXICOLOGY

In single-dose and repeat dose toxicology studies performed under GLP, ublituximab displayed a safety profile similar to what might be expected for anti-CD20 monoclonal antibodies. Single administration of up to 100 mg/kg ublituximab in cynomolgus monkeys was well tolerated, with no local irritation with intravenous administration. Genotoxicity studies (Ames test) showed that ublituximab was not mutagenic. Monkeys that received a single injection of 0.3 mg/kg of ublituximab developed an anti-ublituximab response, whereas anti-ublituximab antibodies were not detected in the animals which received 10 or 100 mg/kg (see Ublituximab Investigator Brochure).

1.3.2 CLINICAL DEVELOPMENT OF UBLITUXIMAB

Ublituximab has been studied in a variety of subject populations, both as a single agent, and in combination with other agents, with over 100 subjects having received ublituximab therapy to date across all studies. Two Single-Agent Phase I/Ib trials have been conducted with ublituximab treating both NHL and CLL subjects, with a total of 41 subjects with relapsed or refractory CLL having been treated with single-agent ublituximab (TG-1101). Further, following demonstration of safety and tolerability in these early single agent studies, Phase I and II combination studies were undertaken with a variety of agents. Given the number of subjects who have received ublituximab in early-phase trials, the safety and side effect profile of the agent is well characterized. Summaries of the single-agent experience are provided below as well as data with use of ublituximab in combination with ibrutinib.

In a two part, first-in human dose escalation study (protocol CD20-0703), subjects with relapsed or refractory CLL received one weekly infusion of single agent ublituximab for 4 doses in a 3+3 dose escalation design through 5 sequential dose levels. Part II of the study was a dose-confirmation component which used an initial dose of 150 mg followed by 7 doses of 450 mg (total dose 3300 mg) – the clinical summary will focus on the Part II part of the study as the dose is more relevant to the clinical application used in current clinical studies. In Part II, 12 subjects were enrolled at 9 centers in France and followed for 12 months. Demographic data for the 12 subjects enrolled in the study were as follows. The median age was 69.5 years [62–77]; median time from diagnosis to inclusion was 10.4 years [4.0–23.6] and median prior therapies was 3 [1–8]. Seven subjects (58%) received at least one prior rituximab-containing regimen. The median lymphocyte bone marrow infiltration was 85% [40–94].

Most frequent drug-related adverse events (AE's) reported were infusion related reactions (IRR) (75% of the subjects, including 33% of subjects with Grade 3 IRR). Other Grade 3/4 AE's > 10% included: neutropenia (67%) and increase ALT/AST (17%). All AEs were reversible spontaneously or with supportive care intervention. None of the reported adverse events were considered as a dose-limiting toxicity according the judgment of the study Safety Committee. Therefore, the maximum tolerated dose was not reached in this study. Significant blood lymphocyte depletion was observed in all subjects: median lymphocyte count at baseline was 46.6 ($\times 10^9/l$); after 1 month (M1) = 1.5 ($\downarrow 94\%$); M4=1.4 ($\downarrow 91\%$) and M6=2.0 ($\downarrow 89\%$). No cases of serum anti-ublituximab antibodies were detected at any time point.

Clinical response was based on the criteria established by the National Cancer Institute (NCI)-Working Group updated in 2008 (Hallek M, 2008). All subjects but one received the planned 8 infusions without any dose reduction--one subject was prematurely withdrawn due to a concomitant secondary leukemia unrelated to ublituximab therapy. Response was evaluated at month 4 for the 11 evaluable subjects, with an initial response rate of 64% (7/11) with a confirmed response at month 6 in 5/11 subjects (45%) subjects (all PRs). Four of the 11 subjects achieved stable disease. At the 1 year follow-up, no responders had progressed, demonstrating all confirmed responses were durable despite no ublituximab maintenance therapy. The median progression-free survival (PFS) was not reached at the 12 month follow-up (Cazin B, 2013).

A Phase I trial of ublituximab (NCT01647971) was subsequently undertaken in subjects with B-cell lymphoma who were relapsed or refractory to a prior rituximab containing regimen, which included 8 subjects with CLL. This trial utilized a 3+3 design, assessing dose levels of 450, 600, 900, and 1200 mg. No DLTs were observed amongst the 12 subjects enrolled into the dose-escalation component, and expansion cohorts were subsequently undertaken at 600, 900, and 1200 mg. Subjects with CLL were eligible to enroll into the expansion cohorts at 600 and 900 mg, receiving ublituximab on days 1, 8 & 15 of Cycles 1 & 2, with monthly maintenance infusions starting in Cycle 3, followed by every 3 months starting in Cycle 6.

Of the 8 CLL subjects enrolled, 4 had infusion related reactions that were manageable with infusion interruptions only and all subjects received all scheduled doses. Other observed adverse events which were considered at least possibly related to study drug included neutropenia Grade 1/2 (n=1) and Grade 3/4 (n=3), as well as thrombocytopenia Grade 1/2 (n=1) and Grade 3/4 (n=1). Six subjects were evaluable for efficacy as of data cutoff for ASCO 2014, with 4 out of 6 subjects achieving a partial response. Rapid and profound circulating lymphocyte depletion (> 50% reduction) was noted with median time to peripheral response of 1 day (O'Connor OA, 2014).

1.3.2.1 PHARMACOKINETICS

After infusion of ublituximab (previously known as LFB-R603) at a 150 mg dose followed by seven weekly injection infusions at 450 mg, results suggested non-linear pharmacokinetics with respect to dose (450 mg vs. 150 mg) and time (week 4 vs. week 8) and more than proportional increase of Cmax and AUC ∞ due to a clearance decrease. The volume of distribution at steady state was small (~5 L), approximately equal to blood volume. These non-linear pharmacokinetics may be explained by binding of ublituximab to its target, with a large component of target-mediated elimination after the first dose that is decreased after subsequent infusions due to a reduction in the available target. However, limited data for each dose level cohort and considerable variability in baseline subject characteristics, particularly in terms of tumor burden, make firm conclusions difficult.

The linear mean serum concentration-times profile after the first, the fourth and the eighth infusion of ublituximab are presented in Figure 4. A summary of non-compartmental PK parameters after the first, the fourth and the eighth infusion of ublituximab are presented in Table 1.

FIGURE 4: LINEAR MEAN SERUM CONCENTRATION-TIMES PROFILE AFTER THE FIRST, THE FOURTH AND THE EIGHT INFUSION OF UBLITUXIMAB

[figure not shown]

TABLE 1: PHARMACOKINETIC RESULTS AFTER THE 1ST (150 MG), THE 4TH (450 MG) AND THE 8TH (450 MG) INFUSION OF UBLITUXIMAB

PK Parameters ^a	1 st Infusion 150 mg (Day 1)	4 th Infusion 450mg (Day 22)	8 th Infusion 450 mg (Day 50)
N	12	11	11
C _{max} (mg/L)	23.4 ± 11.2	168.6 ± 61.8	220.5 ± 141.9
t _{max} (h)	9.0 (5.0-30.3)	5.00 (3.1-52.0)	5.1 (3.1-23.5)
AUC _∞ (mg.h/L)	732.1 ± 590	17890 ± 17730*	50760 ± 74460
t _{1/2term} (h)	13.43± 10.2	80.7 ± 58.5*	147.8 ± 133.8
CL (mL/h)	424.2 ± 389.3	57.69 ± 42.91	38.62 ± 26.63
V _d /V _{dss} , (L)	4.8 ± 2.1	4.9 ± 2.3*	5.7 ± 3.3

^a mean ± SD, t_{max} median (range) , with respect to the start of infusion

*Accurate determination not possible

Concentration was still measurable in at least one subject of the cohort up to day 169. Values for C_{max} and AUC_∞ increased from the first to the eighth infusion whereas t_{1/2} term decreased.

1.3.3 RATIONALE FOR THE PHASE 2 TRIAL

Treatment for newly diagnosed FL and SLL routinely includes chemotherapy based combinations, usually with a monoclonal antibody (Rituxan + Bendamustine or other chemo based regimens). Although effective, these chemotherapy- based regimens will often lead to relapse and unfavorable toxicities, especially for elderly subjects. New, novel treatments are needed which can be used in combination with monoclonal antibodies, that are chemotherapy-sparing with convenience of oral daily dosing.

Umbralisib is a highly-specific and orally available phosphoinositide-3-kinase (PI3K) delta (δ) inhibitor with nanomolar inhibitory potency, and high selectivity over the alpha, beta, and gamma Class I isoforms of PI3K. Umbralisib has been safely administered in subjects with various hematologic malignancies at doses up to and including 1200 mg QD.

Ublituximab (TG-1101) is a glycoengineered monoclonal antibody that binds to the trans-membrane antigen CD20 found on B-lymphocytes. The binding of ublituximab induces an immune response that causes lysis of B cells.

Ongoing studies are evaluating the ublituximab + umbralisib in subjects who previously relapsed from or are refractory to anti-CD20 antibody therapy as well as PI3K delta inhibitor therapy (Lunning, et. al. ASCO 2015, Fowler, et. al. ASCO 2015). A Phase 3, randomized study (UTX-TGR-304)

to assess efficacy and safety of ublituximab + umbralisib compared to obinutuzumab + chlorambucil in subjects with treatment naïve and relapsed/refractory CLL is currently ongoing with no observed safety trends reported (DSMB September 2018) in over 600 patients. To date, ublituximab and umbralisib either as single agents or in combination have been administered to over 1000 subjects worldwide.

As most trials to date have evaluated previously treated subjects, this trial will now evaluate umbralisib + ublituximab in treatment naïve FL and SLL subjects.

2 OBJECTIVES AND ENDPOINTS

2.1 STUDY OBJECTIVES

PRIMARY OBJECTIVE

- To assess the overall response rate (ORR) in subjects with treatment naïve follicular lymphoma (FL) and small lymphocytic lymphoma (SLL) treated with umbralisib in combination with ublituximab.

KEY SECONDARY OBJECTIVES

- To evaluate the safety of umbralisib in combination with ublituximab.
- To assess the duration of response (DOR), Complete Response (CR) and progression-free survival (PFS) in subjects with treatment naïve follicular lymphoma and small lymphocytic lymphoma treated with umbralisib + ublituximab.

2.2 EFFICACY ENDPOINTS

Progression-free survival (PFS)

PFS is defined as the interval from Cycle 1/Day 1 to the earlier of the first documentation of definitive disease progression or death from any cause. Definitive disease progression according to the Revised Response Criteria for Malignant Lymphoma (Cheson et al. 2007).

Overall response rate (ORR)

ORR is defined as sum of CR and PR rates

Complete Response (CR) Rate

CR rate is defined as the proportion of subjects who achieve a CR.

Duration of response (DOR)

DOR is defined as the interval from the first documentation of CR or PR to the earlier of the first documentation of definitive disease progression or death from any cause.

3 ELIGIBILITY CRITERIA

Subjects must meet all of the following inclusion criteria and none of the exclusion criteria to be eligible for participation in this study.

3.1 INCLUSION CRITERIA

Subjects must meet all of the following inclusion criteria to be eligible for participation in this study:

1. Treatment naïve, histologically-confirmed diagnosis of Follicular Lymphoma (FL) Grade 1, 2, or 3a, or Small Lymphocytic Lymphoma (SLL).
2. Subjects must have measurable or evaluable disease, and must have documented evidence for requiring treatment (bulky disease (>5 cm), high LDH, B symptoms, threatened organ function, splenomegaly, cytopenias due to lymphoma, or effusions).
3. Adequate organ system function, defined as follows:
 - a. Absolute neutrophil count (ANC) $\geq 0.75 \times 10^9/L$. **Note:** No growth factors or transfusions are allowed to meet eligibility criteria.
 - b. Platelets $\geq 50 \times 10^9/L$. **Note:** No growth factors or transfusions are allowed to meet eligibility criteria.
 - c. Total bilirubin ≤ 1.5 times the upper limit of normal (ULN) with the exception of Gilbert's Disease and Autoimmune Hemolytic Anemia.
 - d. Alanine aminotransferase (ALT) and aspartate aminotransferase (AST) $\leq 2.5 \times$ ULN if no liver involvement or $\leq 5 \times$ the ULN if known liver involvement
 - e. Creatinine ≤ 2.0 mg/dL OR calculated creatinine clearance (as calculated by the modified Cockcroft-Gault formula using ideal body mass [IBM] instead of mass) ≥ 30 mL/min
4. ECOG performance status ≤ 1 .
5. Patients must be ≥ 18 years of age.
6. Ability to swallow and retain oral medication
7. Female patients who are not of child-bearing potential, and female patients of child-bearing potential who have a negative serum pregnancy test within 72 hours prior to initial trial treatment. Female patients of child-bearing potential and all male partners must consent to use a medically acceptable method of contraception throughout the study period and for 4 months after the last dose of either study drug.
8. Willingness and ability to comply with trial and follow-up procedures.

3.2 EXCLUSION CRITERIA

Subjects who meet any of the following exclusion criteria are not to be enrolled to this study:

1. Subjects currently receiving systemic cancer therapy or previously received systemic cancer therapy for their lymphoma (i.e., chemotherapy, immunotherapy, biologic therapy, hormonal therapy, surgery, transplant, and/or tumor embolization).
2. Evidence of chronic active Hepatitis B defined as Hepatitis B surface antigen positive or Hepatitis B DNA positive by PCR (HBV, NOT including subjects with prior hepatitis B vaccination who are Hepatitis B surface antibody positive only;) or chronic active Hepatitis C infection (HCV) defined as Hepatitis C RNA positive by PCR, cytomegalovirus (CMV) DNA positive by PCR, or known history of HIV. If HBc antibody, HCV antibody or CMV IgG and/or IgM antibody is positive, subjects must be evaluated for the presence of HBV, HCV, or CMV by PCR - See Appendix F.
3. Subject has received wide field radiotherapy (including therapeutic radioisotopes such as strontium 89) \leq 28 days or limited field radiation for palliation \leq 14 days prior to Cycle 1/Day 1 or has not recovered from side effects of such therapy.
4. Primary central nervous system lymphoma (PCNSL) or known intracranial involvement, or leptomeningeal metastases.
5. Ongoing immunosuppressive therapy including systemic corticosteroids. Subjects are allowed to use topical or inhaled corticosteroids.
 - a. Corticosteroid therapy started at least 7 days prior to Cycle 1/Day 1 (prednisone \leq 10 mg daily or equivalent) is allowed as clinically warranted.
6. Known history of drug-induced liver injury, alcoholic liver disease, non-alcoholic steatohepatitis, primary biliary cirrhosis, ongoing extrahepatic obstruction caused by stones, or cirrhosis of the liver.
7. Any severe and/or uncontrolled medical conditions or other conditions that could affect their participation in the study such as:
 - a. Symptomatic, or history of documented congestive heart failure (New York Heart Association functional classification III-IV)[see Appendix C- NYHA Classifications]
 - b. Significant cardiovascular disease such as uncontrolled or symptomatic arrhythmias, congestive heart failure, or myocardial infarction within 6 months of enrollment.
 - c. Concomitant use of medication known to cause QT prolongation or torsades de pointes should be used with caution and at investigator discretion.
 - d. Poorly controlled or clinically significant atherosclerotic vascular disease including cerebrovascular accident (CVA), transient ischemic attack (TIA), angioplasty, cardiac or vascular stenting within 6 months of enrollment.
8. Malignancy other than Follicular Lymphoma or SLL within 3 years of study enrollment except for adequately treated basal, squamous cell carcinoma or non-melanomatous skin cancer, carcinoma in situ of the cervix, superficial bladder cancer not treated with intravesical chemotherapy or BCG within 6 months, localized prostate cancer and PSA <1.0 mg/dL on 2 consecutive measurements at least 3 months apart with the most recent one being within 4 weeks of Cycle 1/Day 1.
9. Women who are pregnant or lactating.

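### Exclusion 8 gives the PSA limit for localized prostate cancer in mg/dL; 1.0 mg/dL is 10,000 ng/mL, so the numeric cut-off has no practical effect as written

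*Combined protocol and SAP*

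**What the plan says.** Exclusion 8 in Section 3.2 opens: "Malignancy other than Follicular Lymphoma or SLL within 3 years of study enrollment except for adequately treated basal". A list of further exceptions follows. The last is "localized prostate cancer and PSA <1.0 mg/dL on 2 consecutive measurements at least 3 months apart", and it is completed by a recency condition: "with the most recent one being within 4 weeks of Cycle 1/Day 1".

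The Synopsis repeats the criterion with the same number and unit, so the two statements agree with each other. The protocol gives PSA in no other unit and supplies no reference range or conversion. PSA does not appear in the assessment schedule (Section 5) or in the local and central laboratory lists (Sections 5.1.1 and 5.1.2). Exclusion 8 is therefore the only place where a PSA value decides anything.

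**The concern.** The criterion asks for two consecutive values, separated by at least 3 months, with the later one recent. That is how one would test for sustained and current control of the disease. A threshold serves that test only if it lies within the range of values that patients actually have. A limit in mg/dL looks far outside that range for a marker conventionally reported in ng/mL.

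If so, the numeric part of a binding eligibility rule does no work. A man with recent localized prostate cancer and a clearly raised PSA on both occasions would fall within the exception, and criterion 8 would not exclude him. Progression-free survival counts death from any cause (Section 2.2), so an uncontrolled competing cancer bears on a secondary endpoint as well as on the subject.

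**Working it through.** The limit is a fixed eligibility value, not one derived from other inputs, so the plan has no calculation to reproduce. The check is a unit conversion.

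**Inputs**
- Limit: PSA < 1.0 mg/dL (exclusion 8, Synopsis and Section 3.2).
- 1 mg = 1,000,000 ng; 1 dL = 100 mL.
- Assumption: laboratories report PSA in ng/mL. This is common convention and is not in the documents.

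**Step 1. Convert the limit.**

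1.0 mg/dL = 1,000,000 ng / 100 mL = 10,000 ng/mL (equivalently 10 µg/mL, or 10 mg/L).

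**Step 2. Convert in the other direction.**

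1.0 ng/mL = 100 / 1,000,000 mg/dL = 0.0001 mg/dL. The written limit is therefore 1.0 / 0.0001 = 10,000 times the same number read in ng/mL.

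**Step 3. Apply the written limit to a range of values.** The last column is for scale only and is not put forward as the right threshold.

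| PSA (ng/mL) | PSA (mg/dL) | Below 1.0 mg/dL, as written? | Below 1.0 if read in ng/mL? |
|---|---|---|---|
| 0.1 | 0.00001 | yes | yes |
| 1 | 0.0001 | yes | no |
| 4 | 0.0004 | yes | no |
| 10 | 0.001 | yes | no |
| 100 | 0.01 | yes | no |
| 1,000 | 0.1 | yes | no |
| 5,000 | 0.5 | yes | no |
| 9,999 | 0.9999 | yes | no |
| 10,000 | 1.0 | no | no |

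Every value up to 9,999 ng/mL meets the written limit; the first to fail is 10,000 ng/mL.

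**Step 4. Separate the number from the rest of the exception.** Three conditions do not depend on the unit: the cancer must be localized, there must be two consecutive measurements at least 3 months apart, and the latest must fall within 4 weeks of Cycle 1/Day 1. With the written limit, the second and third establish that PSA was measured twice and recently. They do not establish that it was low.

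**The case against.** The strongest case on the other side accepts the conversion and disputes the consequence.

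- **The criterion as a whole is not empty.** A reader might infer that exclusion 8 screens out nobody with prostate cancer. The documents do not support that. Another malignancy within 3 years still excludes unless an exception applies, and the prostate exception keeps its three other conditions. Exclusion 7 also bars severe or uncontrolled medical conditions that could affect participation, which lets an investigator refuse a man whose cancer is plainly active. This stands, and it confines the point to the numeric cut-off.
- **Misread scans.** A reader might infer that nodal or bone spread from prostate cancer would be counted as lymphoma. The exception covers localized disease only, so spread known at entry is outside it in any unit. Lymphoma must be histologically confirmed for entry (Section 3.1), and new FDG uptake at an unaffected site needs confirmation by other modalities (Section 8.4.4). Later spread is possible, but nothing in the documents allows its effect to be sized.
- **Second-malignancy reporting.** A reader might infer that the special-interest signal would be distorted. Under Section 10.9.5 a condition present at entry is medical history and becomes an adverse event only if it worsens, so the link is weak.
- **Divergence between sites.** Some of the up to 15 sites might correct the unit silently while others apply it literally. The documents do not show how sites read the limit. A site with a result in ng/mL may well notice the mismatch and query it. This is conjecture and carries no weight here.
- **The ng/mL convention and the intended value are not in the documents.** Correct. The convention has to be labelled an assumption. The documents also cannot show that the number 1.0 is right and only the unit is wrong, so calling the limit 10,000 times too permissive would go further than they allow.

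What survives is that a binding threshold, stated identically in two places and corrected nowhere, cannot do what its surrounding conditions are built to do. That investigators may recognise the slip is not a control.

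**Conclusion.** Wrong as written, minor reach. The conversion to 10,000 ng/mL is exact. That the cut-off therefore admits any realistic PSA, and cannot demonstrate controlled disease, rests on two assumptions: PSA is reported in ng/mL, and values near 10,000 ng/mL are very rare. The documents give no PSA range, but the distance between ordinary values and the limit in the table leaves little room for another reading.

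The reach is small. The point touches only men with localized prostate cancer within 3 years of enrollment, in a study of up to 50 subjects, and the other eligibility conditions still apply to them. The documents give no count of such men, so no number of affected subjects can be stated. No sample size, endpoint definition, analysis or safety rule changes.

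**What to change.** The sponsor should verify the intended PSA unit. The evident reading is ng/mL, but confirming the unit, and the number that goes with it, is for the sponsor. The corrected text should then appear identically in exclusion 8 of the Synopsis and of Section 3.2, and in any eligibility checklist or data-entry check derived from them. The documents do not show such checks, so whether they carry the same unit has to be looked up. It would also be sensible to see whether anyone already enrolled entered under this exception, and on what PSA values.

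The cost is one unit corrected in two places, which can go into the next protocol amendment. It adds no procedure and does not affect the sample size or the analysis.
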